Objective 2: Determine short-interval pregnancy, satisfaction, and continuation rates among women who received contraceptives in the home versus those that sought postpartum contraceptives through routine care.

Objective 3: Determine short-interval pregnancy, satisfaction, and continuation rates among women who opted for long-acting versus short-acting reversible contraceptives that were provided in the home setting.

Objective 4: Document side effects and adverse events occurring in the study population.

Methodology:

Study Design: This study is a cluster randomized trial of an intervention to increase uptake of postpartum contraception by providing them to women in their home and observe the effect on uptake in the community of interest. We have eight communities involved the healthcare services provides by the CHD that will be combined into six clusters, for study purposes. The clusters are independent of one another, except that some nurses offering the contraceptives may cover more than one cluster. Patients may also move between clusters over the course of the trial. Women will be recruited for enrollment into the CHD, and subsequently the study, blind to whether their cluster will be offered home-based contraception in the postpartum setting.

Operational Definitions/Proposed Intervention: This is a prospective community cluster-randomized study of a home-based intervention to increase uptake of postpartum contraceptives and study the direct effect on short-interval pregnancy, continuation, and satisfaction rates. The study has two phases.

Phase 1: The first phase fulfills AIM 1 and will involve a cluster randomized trial of the intervention, which is to bring and offer Jadelle[®], among all other routine postpartum contraceptive options, to the women in their homes, compared to routine care. Currently, around 4% of the population opts for Jadelle[®], which is less than expected, likely due to the fact that previously, Jadelle[®] was only offered

at a clinic inconvenient to the study population that required significant time and travel costs. Recently, implant availability has increased in the region due to the work of a non-governmental organization, and the nurses within the CHD were trained on implant placement. Therefore, Jadelle®, which was previously offered as part of the standard of care but not routinely available, now is accessible.

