Based on previously collected data, we expect that during our study timeframe around 260 women will meet eligibility criteria over the course of one year. The clusters will be randomly assigned by a biostatistician. This study, with 200 women enrolled (100 from intervention clusters and 100 from control clusters) will be powered to detect a change in Jadelle uptake rates from 3% to 15% at 85% power and 5% significance, with an intra class correlation of 2%.

[figure not shown]
Group	Proportion Positive	N Per Group	Standard Error	95% Lower	95% Upper
Population 1	0.03	100			
Population 2	0.15	100			
Rate Difference	-0.12	200	0.04	-0.20	-0.04

Alpha= 0.050, Tails= 2, Power = 0.848

Power computation: Normal approximation (unweighted mean p)
Precision computation: Log method

Phase II: Phase two of the study are six month and one-year follow-up visits that occur as part of routine care. Patients are immediately enrolled on delivery into Ninos Sanos, the early childhood health and development program offered through the CHD. Women and infants are seen monthly as part of the program, including routine visits at six and twelve months. At these sessions, mothers will be subject to a questionnaire regarding their contraceptive satisfaction and continuation habits, as well as whether or not they became pregnant since their delivery. This frequent and routine contact will ensure that patients are easily located for performing the follow-up questionnaire, but also will have no problem contacting study personnel if they have issues with their contraception or to report adverse events. We will also hold a focus group (interviews and surveys) for providers regarding their comfort and satisfaction with provision of care in the home setting before the study begins and after enrollment is complete.

Study Flow Diagram:

Study Visits: Patients who participate in the Community Health Services program through the CHD receive routine antepartum counseling on postpartum contraception in their home. At this visit, which is part of routine care, all women receive an educational intervention on contraception, which includes Jadelle® and the risks/side effects, benefits, and alternatives to the immediate postpartum implant.

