Visit 1: At the postpartum visit in their home, patients will be enrolled in the study and provide informed consent. Once they have agreed to participate in the study, they will be offered postpartum contraception in the home in the intervention group, and through routine care (at CHD pharmacy or clinic location) in the control group. The nurses will bring all routinely available medications to the patient's home for those in the intervention clusters, including pills, condoms, Jadelle®, and depot medroxyprogesterone acetate. Patients who are breastfeeding will not be offered estrogen-containing methods. Participants in both the intervention group and control group will also be offered IUD placement; regardless of group, they will need to present to an area clinic setting for placement should they choose this method. Women opting for Jadelle® will receive immediate implant placement, and women that opt for other methods will receive their method of choice. 99% of patients in the community service program are seen for this postpartum visit, which is part of the standard of care for patients in this region.

Ninos Sanos Visits: The follow-up visits will occur through routine care as part of the Ninos Sanos program, into which all patients in the Madres Sanas program are automatically enrolled. Mothers are seen with their infants monthly in their home, including visits at six and twelve months after delivery. At these routine visits, the mothers enrolled in the study, in both groups, will complete a survey. The surveys will assess patient continuation rates and satisfaction with the contraceptive method of choice. Patients will also be queried about side effects such as: irregular bleeding, weight gain, headaches, rash, chest pain, moodiness, insertion site pain, cramps, acne, nausea, hair loss, or issues with breastfeeding after device placement. All patients will be questioned regarding repeat

pregnancy at these visits, as well, including outcomes of repeat pregnancies such as delivery, termination of pregnancy, or spontaneous abortion. We anticipate that this survey will take about 10 – 20 mins to administer. Additionally, the study nurses will perform a survey of their comfort and satisfaction with administering contraception in the home, which will be performed after enrollment is complete. These questionnaires are included with the submission.

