The same community health nurses who collect the database information and provide the clinical care will be trained in the consent, enrollment, and implant placement process for this study. During the postpartum visit, after a woman has completed her routine evaluation, the community health nurse will invite the woman to participate in this study. If she is not interested, it will not affect her involvement in the community program, she will receive care as usual. If she is interested, then the procedure for obtaining consent will be followed. While women can be enrolled in the clinical care database at any point during their pregnancy, the program entails four visits, ideally at <12 weeks, 13-28 weeks, 29-35 weeks, >36 weeks. During these visits information on health and pregnancy history are obtained as well as measurements of weight, fetal heart rate, fundal height, and blood pressure. Community health nurses come in contact with these women multiple ways: word of mouth, self-referral, referral through other CHD programs.

Procedures to Ensure Ethical Research: In order for the study to move forward as planned, it will require approval from numerous ethics organizations. These include the Colorado Multiple Institutional Review Board, the University Francisco Marroquin Institutional Review Board, and the Community Advisory Board for Research from the SW Trifinio region in Guatemala. These multiple levels of review will ensure that the research is culturally appropriate, that researchers are sufficiently qualified and expert to perform the proposed research, that the logistics of the international nature of the project are well planned and executed, and that dissemination of results back to the community is performed.

Patients are consented for this study at the postpartum visit. The patients participating in the cluster randomized trial will participate in a questionnaire at their six month and one year pediatric visits for the infant they delivered at enrollment into the study. Risks involved with the questionnaire are that patients may not want to answer questions about their contraceptive

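### Nurses may cover more than one cluster and nothing keeps such clusters in the same arm, so home supply could reach control women and dilute the uptake contrast

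*Combined protocol and SAP*

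**What the plan says.** Under Methodology, Study Design, eight communities are combined into six clusters. Their independence carries an exception: "The clusters are independent of one another, except that some nurses offering the contraceptives may cover more than one cluster". The next sentence adds: "Patients may also move between clusters over the course of the trial".

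On allocation, Phase 1 says "The clusters will be randomly assigned by a biostatistician". The Timeline gives three intervention and three routine-care clusters. No restriction on the draw is described.

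Under Visit 1, the arms are separated by place of supply. For the intervention arm, "The nurses will bring all routinely available medications to the patient's home for those in the intervention clusters". Controls are offered contraception after consent too, "and through routine care (at CHD pharmacy or clinic location) in the control group". In both arms an IUD requires a clinic visit, and all women receive the same antepartum counselling.

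On training, Phase 1 says that "the nurses within the CHD were trained on implant placement". Procedures for Data Collection & Quality Control says that the community nurses who provide care and collect the data "will be trained in the consent, enrollment, and implant placement process for this study". Neither statement is limited to one arm.

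Home contact continues in both arms after enrolment. Under Ninos Sanos Visits: "Mothers are seen with their infants monthly in their home".

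**The concern.** The treatment contrast depends on what a nurse does at a home visit. A nurse whose clusters fall in opposite arms supplies contraceptives at home in one and is meant to direct women to the pharmacy or clinic in the other. She is trained to place implants and handles stock for part of her work. The protocol blinds women to their cluster's assignment at recruitment, but says nothing similar about nurses.

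If some control women are supplied at home, control uptake rises and the difference between arms shrinks. The trial could then miss a real effect, and a null result could not be told apart from poor separation of the arms. As the plan stands, leakage could not even be counted: no record of home supply in control clusters is described. No time window is set for uptake either, so with monthly home visits the exposure need not end at the first postpartum visit.

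**Working it through.** **Inputs from the protocol.** Six clusters, three per arm (Timeline). 100 women per arm, Jadelle uptake 3% v 15%, two-sided 5% significance, power 0.848 and intra-class correlation 2% (Phase 1). The number of shared nurses and the leakage rate are not given.

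**Chance that a shared pair is split.** There are C(6,3) = 20 allocations.
- One pair sharing a nurse: it is split in 2 × C(4,2) = 12 of 20 (60%) and kept together in the other 8.
- Two separate pairs, both kept together: they must lie in opposite arms, each with one of the two remaining clusters, so 2 × 2 = 4 of 20. At least one pair is split in 16 of 20 (80%).
- Three separate pairs: an arm of three clusters cannot be made of whole pairs, so no allocation keeps all three together.

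**The plan's own power.** With mean p̄ = (p₁ + p₂)/2, SE₀ = √(2p̄(1 − p̄)/n) and SE₁ = √([p₁(1 − p₁) + p₂(1 − p₂)]/n), power = Φ((p₂ − p₁ − 1.96·SE₀)/SE₁). For 3% v 15% and n = 100, SE₀ = 0.0405 and SE₁ = 0.0396, so power = Φ((0.12 − 0.0793)/0.0396) = 0.848. This matches the plan and assumes a clean 3% control rate.

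**With leakage.** Let c be the assumed share of control women who receive the home offer and take up Jadelle at the planned 15%. The control rate is 3% + 12c points and the difference is 12(1 − c) points. The last column divides n by the design effect 1 + (33.3 − 1) × 0.02 = 1.647, using the plan's own intra-class correlation and 100/3 = 33.3 women per cluster.

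| c (assumed) | Control v intervention | Difference | Power, plan's formula | Power with design effect |
|---|---|---|---|---|
| 0 | 3.0% v 15% | 12.0 points | 85% | 64% |
| 10% | 4.2% v 15% | 10.8 points | 74% | 52% |
| 20% | 5.4% v 15% | 9.6 points | 61% | 41% |
| 30% | 6.6% v 15% | 8.4 points | 48% | 32% |

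The fall from 85% to 64% in the first row comes from clustering, which is a separate matter. The effect of leakage is read down each column.

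**What these values of c require.** Suppose one pair is split, clusters are of equal size and leakage occurs only through that nurse. Leakage is then confined to one control cluster of about 33 women. c = 10% means supplying 10/33.3 = 30% of that cluster at home, c = 20% means 60%, and c = 30% means 90%. The upper end is a bad case unless more than one control cluster shares a nurse with the intervention arm.

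**The case against.** The strongest reply is that the protocol already ties supplies to intervention homes. A nurse may serve two clusters on different days and have no stock with her in control homes. That is fair. A reader might infer that shared nurses will carry implants, injections and pills through control homes, but the documents do not say so. They also do not say that any nurse will span arms. They leave the route open, without a safeguard or a record.

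A reader might also infer from the sentence on women moving that movers contaminate the uptake comparison. The documents do not support this. Consent, enrolment and the offer all take place at the postpartum home visit, so a woman who moved before it enters in the cluster where she is visited. Moves after it bear mainly on the 6- and 12-month outcomes.

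Two further points stand. Shared nurses have a benefit: they balance nurse skill across arms, whereas nurses confined to one arm are confounded with it. And restricting the draw is not free. With two shared pairs only 4 allocations remain, and a two-sided randomisation test, counting the mirror-image allocation as equally extreme, could not give p below 2/4 = 0.5. The limit is already 2/20 = 0.1 for the unrestricted draw. The plan names no such test, but the count shows how little randomisation is left.

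It would also be too strong to say that analysis can do nothing about leakage. If place of supply is recorded, a sensitivity analysis is possible. As written, no such record is planned.

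**Conclusion.** The concern holds as an open and uncontrolled route for leakage, not as a demonstrated fault in delivery. The protocol itself names shared nurses as an exception to cluster independence and provides nothing to contain it. If one pair of clusters shares a nurse, an unrestricted draw is more likely than not (60%) to split it.

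The likely bias is towards no difference, so the threat is to power and to the size of the estimate, not of a false positive. For c between 10% and 30%, the Jadelle difference falls by 1.2 to 3.6 points and power on the plan's formula drops to between 74% and 48%. This rests on an assumed c and on full response among the control women reached. The factor (1 − c) would apply in the same way to contraceptive uptake overall, the named primary outcome, but the plan gives planning rates only for Jadelle.

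**What to change.** 1. **Clusters and allocation.** When merging the eight communities into six clusters, put communities served by the same nurse in one cluster. Where clusters still share a nurse, either roster each nurse to one arm or restrict the draw so that those clusters fall in the same arm. Use the restriction only as far as enough 3 v 3 allocations remain: 8 of 20 with one shared pair, 4 with two separate pairs, none with three.
2. **Recording.** For every woman in both arms, enter in REDCap the nurse who made the postpartum visit and the place of supply (home, pharmacy or clinic). Report the share of control women supplied at home and examine it in a sensitivity analysis.
3. **Movers.** State that each woman is analysed by the cluster in which she was enrolled at the postpartum visit, even if she moves afterwards. This matters mainly for continuation and short-interval pregnancy at 6 and 12 months.

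**Cost.** A review of nurse coverage and an instruction to the biostatistician before the draw, two data fields, and one sentence in the analysis plan. No need for extra staff is evident, but the documents give no nurse numbers or routes, so the rostering must be checked locally. The downsides are fewer admissible allocations and nurses nested within one arm. If these are judged too costly, items 2 and 3 and the grouping of communities are still worth doing.

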Study Title: A cluster randomized trial of a home-based intervention to increase uptake of postpartum contraceptives and its effect on short-interval pregnancy rates in a postpartum population of rural Guatemalan women

Principal Investigator: [name]

COMIRB No: 17-1314

Version: v30-Aug-2017

Summary: This study will involve a home-based intervention to increase uptake of contraception, especially the contraceptive implant, Jadelle®, in a postpartum population in the SW Trifinio region and document how increased uptake affects short-interval pregnancy rates. All contraceptives involved are already in common use in the population.

Problem: Adolescent pregnancy, high fertility rates, and high unmet need for contraception are a significant health sector problem for Guatemala, a Central American country, and are the public health problems of interest in this study [1]. According to the Guttmacher Institute, 11% of Guatemalan females are adolescents (age 15 – 19), 30% report having their sexual debut within this age range, and 22% of them have been married [2]. This study will focus on a sub-population (women age 15 – 35) of women from the rural Southwest (SW) Trifinio region of Guatemala who, according to a needs assessment and several program evaluation studies of the population, are particularly burdened by high fertility rates, high unmet need for contraception, and adolescent pregnancy [1]. The average birth spacing interval in this population is unknown [1]. Four percent of patients currently opt for Jadelle® as their birth-spacing method of choice, and the reported pregnancy rate in this group is unknown [1].

Significance and Use of Results: The previously mentioned research details the experience of North American populations living in a high-income country with access to healthcare resources. The objective of this research proposal is to study how improving access and delivery of contraception postpartum, by providing it in the home setting, can increase postpartum contraceptive uptake and reduce repeat pregnancy among a high-risk Central American rural population of women. No studies currently exist in the literature on interventions to increase postpartum contraceptive use in Guatemala. Information gleaned from this study will be used to learn more about the study population and subsequently perform additional studies aimed at increasing postpartum contraceptive use.

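### The power statement uses an unexplained 3% control implant rate where the protocol reports about 4%; with the 15% target held fixed, power is 76% rather than 85% before clustering, and lower still after it.

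*Combined protocol and SAP*

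**What the plan says.** All references are to the combined protocol and SAP.

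- **Power statement.** Under Methodology (Phase 1), and again under Analysis Plan (Methods & Models), the trial "will be powered to detect a change in Jadelle uptake rates from 3% to 15% at 85% power and 5% significance". The total is 200 women, 100 from each set of clusters, with an ICC of 2%.
- **Software output in Phase 1.** The control row reads "Population 1 0.03 100" and the result line reads "Alpha= 0.050, Tails= 2, Power = 0.848". The method given is a normal approximation using the unweighted mean proportion.
- **Baseline in the Problem section.** "Four percent of patients currently opt for" Jadelle. This figure is cited to an unpublished qualitative assessment.
- **Baseline in Phase 1.** "Currently, around 4% of the population opts for" Jadelle. The text attributes the low figure to past provision at an inconvenient clinic and continues: "Recently, implant availability has increased in the region due to the work of a non-governmental organization". It adds that the programme's nurses have been trained in placement and that the implant is now accessible.
- **Clusters.** The Study Design section gives six clusters, and the Timeline puts three in each arm.

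No section derives the 3% or says why it lies below the reported 4%.

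**The concern.** The power statement describes a change from a starting rate, and the only starting rate reported elsewhere is about 4%. Power for an uncommon outcome is sensitive to the control rate, and here the unexplained departure goes in the favourable direction. The text on improved access gives no reason to expect a rate below 4%.

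Implant uptake is the only outcome with a power statement. If the trial finds no difference, readers will judge that result against a claimed 85%. The baseline question is separate from the missing allowance for clustering: correcting only the clustering would still leave a figure resting on the unexplained 3%.

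**Working it through.** **Inputs.** From Phase 1: 100 women per arm, intervention rate 15%, two-sided alpha 0.05, control rate 3%, ICC 0.02. From the Problem section and Phase 1: current use about 4%. From Study Design and the Timeline: six clusters, three per arm.

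**Formula (no clustering).** Let p̄ be the mean of the two rates.

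SE₀ = √[2p̄(1 − p̄)/n]

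SE₁ = √[(p₁(1 − p₁) + p₂(1 − p₂))/n]

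Power = Φ[(p₂ − p₁ − 1.96·SE₀)/SE₁]

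**Step 1: reproduce the plan's figure (3% v 15%).** p̄ = 0.09, SE₀ = 0.04047, SE₁ = 0.03957. Then (0.12 − 0.07932)/0.03957 = 1.028, and power is 0.848. This matches the output exactly with n = 100 per arm, so the stated figure contains no design effect.

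**Step 2: change only the control rate (4% v 15%).** p̄ = 0.095, SE₀ = 0.04147, SE₁ = 0.04073. Then (0.11 − 0.08127)/0.04073 = 0.705, and power is 0.760. The number per arm for 85% power rises from 101 to 127.

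**Step 3: how far this depends on the target and on rounding (100 per arm, no clustering).**

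| Control | Intervention | What is held | Power |
|---|---|---|---|
| 3.5% | 15% | target | 80.6% |
| 4% | 15% | target | 76.0% |
| 4% | 16% | 12-point difference | 81.2% |
| 4% | 20% | five-fold ratio | 94.2% |
| 5% (assumed) | 15% | target | 65.6% |
| 6% (assumed) | 15% | target | 54.7% |

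**Step 4: apply the stated ICC.** Mean cluster size is 200/6 = 33.3, taken as equal across clusters. The design effect is 1 + (33.33 − 1) × 0.02 = 1.647, and the effective number per arm is 100/1.647 = 60.7. The formula above with n = 60.7 gives:

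- 3% v 15%: (0.12 − 0.10179)/0.05078 = 0.359, power 64.0%.
- 4% v 15%: (0.11 − 0.10429)/0.05227 = 0.109, power 54.3%.

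**Step 5: allow for three clusters per arm.** With six clusters and two arms, a cluster-level comparison has 6 − 2 = 4 degrees of freedom. The critical value is 2.776 instead of 1.96. Power comes from the noncentral t distribution with noncentrality (p₂ − p₁)/SE₁ at n = 60.7:

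- 3% v 15%: 0.12/0.05078 = 2.363, power about 44%.
- 4% v 15%: 0.11/0.05227 = 2.105, power about 36%.

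From a 4% baseline, the intervention rate detectable with 85% power is about 30% on this basis. The normal approximation with the same design effect gives about 22%, which is too favourable with so few clusters.

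**The case against.** The strongest reply is that the mismatch does not show 3% to be wrong. The 4% is described as a birth-spacing choice among patients, or in the population. The power input is uptake among enrolled postpartum women aged 15 to 35. The documents do not say these are the same quantity, and 3% could be a subgroup rate. That stands, and it is why the criticism is that the figure is unexplained and unreconciled. But if there is such a source, the protocol does not give it.

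A second reply is that the shortfall depends on holding 15% fixed, because the protocol derives neither rate. This also stands as a condition. Keeping the 12-point difference still leaves power short, at 81.2%. The five-fold ratio gives 94.2%, but no such ratio is stated, and 15% is the only target given.

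A reader might go further and infer that improved access has already pushed control uptake to 5% or 6%, so that unclustered power is really 66% or 55%. The documents do not support that. Phase 1 uses 4% as the current figure and quantifies no later rise. Under Visit 1, control women still obtain their method through the pharmacy or clinic. Easier access could also raise uptake in the intervention arm.

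Finally, most of the fall from 84.8% to 54.3% is due to clustering, which alone brings power to 64.0%. The baseline's own contribution is about 9 points before clustering (84.8% to 76.0%) and about 10 after it (64.0% to 54.3%).

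**Conclusion.** The point holds as an unreconciled assumption. It is not an arithmetic error, since 0.848 is correct for the inputs entered. At the protocol's own reported baseline and stated target, 100 per arm gives 76.0% power without clustering. Rounding does not rescue the claim, since 3.5% gives 80.6%. Once the stated ICC is applied, the normal approximation gives 64% at 3% and 54% at 4%. With a t reference suited to three clusters per arm, the figures are about 44% and 36%.

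These results assume that 15% is fixed, that cluster sizes are equal, that the ICC is 2%, and that the reported 4% applies to the women who will be enrolled. Results at control rates above 4% are illustrative only. Correcting this input would not give power for overall contraceptive uptake, which the Analysis Plan names as the primary outcome, because the calculation concerns Jadelle alone.

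**What to change.** In the Phase 1 sample-size text and in Analysis Plan, Methods & Models:

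1. Replace 3% with the documented 4%, or with a sourced rate for the eligible women taken from the programme database before randomisation. Reconcile the chosen figure with the Problem section and the Phase 1 description.
2. Keep 200 women. Restate the power, or the detectable difference, with the design effect applied and a reference distribution that reflects three clusters per arm.
3. State that the 15% target is held fixed.
4. Show power over a range of control rates, with any rate above 4% labelled as an assumption.

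This takes wording changes and one recalculation, with no extra women and no change in procedures. The downside is a visibly less favourable stated power.

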Programs Used: The analysis plan for this will use summary statistics to describe the patient population as well as the outcomes. We will use Student t (normally distributed variables) or non-parametric medians (non-normally distributed variables) tests for continuous data and χ^2 or Fisher's exact tests (for variables with cell sizes <5) for categorical data. Bivariate analyses will be performed to compare the groups. Variables that are significant ($P < 0.05$) in the bivariate analyses will be included in a logistic regression to determine independent predictors of repeat pregnancy. SPSS statistical software (version 24.0.0; IBM SPSS Inc, Chicago, IL) will be used for all the analyses.

References:

2. Guttmacher Institute. Sexual and reproductive health of young women in Guatemala. Online 2014, accessed 1/17/17 (<https://www.guttmacher.org/sites/default/files/factsheet/fb-dd-guatemala.pdf>)
4. LARCs: IUD and Implant Options. Planned Parenthood. Accessed 1/23/17 (<https://www.plannedparenthood.org/planned-parenthood-mar-monte/patient-resources/long-acting-reversible-contraception/larc>)

Timeline: After we have obtained IRAC/COMIRB APPROVAL and Francisco Marroquin University Ethics approval to proceed with the study, we will begin the study. We anticipate the first step of the trial to start January 2018. We expect this to be a 24-month study; the timeline will appear as follows:

Months	Activities
Dec 2017	Training, Jadelle placement refresher course

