Jan – Dec 2018	Study Execution: Intervention in 3 study clusters, routine care in 3 study clusters
January 2019	Data analysis
Jan – Dec 2019	Follow-up Questionnaires: all participants
January 2020	Data analysis

Budget:

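### The 85% power claimed with an ICC of 2% is the power without clustering; with that ICC and the six planned clusters, the same formula gives about 64%

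*Combined protocol and SAP*

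**What the plan says.** The sample size paragraph in Methodology, Phase 1 claims that 100 women from intervention clusters and 100 from control clusters give power to "detect a change in Jadelle uptake rates from 3% to 15% at 85% power and 5% significance, with an intra class correlation of 2" per cent. Analysis Plan, Methods & Models repeats the sentence. It is the only power statement in the document.

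The output under the Phase 1 paragraph lists the two proportions, 100 per group, a standard error of 0.04 and an interval of -0.20 to -0.04. It then reads "Alpha= 0.050, Tails= 2, Power = 0.848" and names its method: "Power computation: Normal approximation (unweighted mean p"). It shows no ICC, number of clusters, cluster size or design effect.

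On the design, Study Design refers to eight communities "that will be combined into six clusters, for study purposes", and the Timeline has "Intervention in 3 study clusters, routine care in 3 study clusters". On recruitment, Phase 1 says "we expect that during our study timeframe around 260 women will meet eligibility criteria" over one year. On analysis, Programs Used plans chi-square tests or Fisher's "exact tests (for variables with cell sizes <5) for categorical data" and states no adjustment for clustering.

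**The concern.** Women in the same cluster share nurses, clinic access and local attitudes, so 100 women in three clusters carry less information than 100 independent women. The sentence tells the reader that this has been allowed for. The printed output suggests that it has not.

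If so, ethics reviewers and readers have been given a power figure the design does not have. A null Jadelle result could then be taken as well-powered evidence that home provision makes no difference, when the trial had a substantial chance of missing the effect it was planned to find.

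**Working it through.** **Inputs.** From the protocol: p1 = 0.03, p2 = 0.15, 100 women per arm, two-sided alpha 0.05, ICC 0.02 (Phase 1); six clusters (Study Design), three per arm (Timeline). Derived: mean cluster size m = 100/3 = 33.3. Assumed: equal cluster sizes, since no individual sizes are given.

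**Step 1: reproduce the printed power.** The formula uses the mean proportion for the null variance and the separate proportions for the alternative variance:

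power = Φ[(|p2 − p1| − 1.96 × SE0) / SE1]

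- Mean p = (0.03 + 0.15)/2 = 0.09.
- SE0 = √(2 × 0.09 × 0.91/100) = 0.0405.
- SE1 = √((0.03 × 0.97 + 0.15 × 0.85)/100) = 0.0396.
- Power = Φ[(0.12 − 1.96 × 0.0405)/0.0396] = Φ(1.028) = **0.848**.

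This matches the print to three decimals. A simple interval for the difference, 0.12 ± 1.96 × 0.0396, runs from 0.042 to 0.198. That agrees with the printed limits to their two decimals, although the output labels its precision calculation a log method. Without clustering the formula needs 101 per arm for 85%, so 100 per arm leaves no room for a design effect.

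**Step 2: apply the stated ICC.**

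- Design effect = 1 + (33.3 − 1) × 0.02 = 1.647.
- Effective n per arm = 100/1.647 = 60.7.
- SE0 = 0.0519; SE1 = 0.0508.
- Power = Φ[(0.12 − 1.96 × 0.0519)/0.0508] = Φ(0.359) = **0.640**.

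The 95% interval around the planned difference, written as in the printed table, becomes -0.22 to -0.02.

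**Step 3: what 85% would take, by the same formula.** The rate detectable from 3% is 20.2%. With three clusters per arm, about 300 women per arm are needed (design effect 2.98, effective n 100.7, power 0.850), against about 260 eligible women in total.

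**Step 4: sensitivity for 3% versus 15%.**

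| Change | Power |
|---|---|
| Other normal-type formulas (unpooled, mean p throughout, arcsine) | 64% to 69% |
| Clusters of 25, as if the eight communities were not combined (design effect 1.48) | 69% |
| All 260 women enrolled (design effect 1.847, effective n 70.4) | 71% |
| ICC 0.01 (assumed) | 74% |
| ICC 0.05 (assumed) | 45% |
| Cluster size CV 0.3 / 0.5 / 0.7 (assumed) | 62% / 60% / 56% |
| t reference on 4 df (six clusters, two arms) | 42% to 44% |

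None of these returns to 85%. On 4 df the rate detectable from 3% is about 28% to 30%, and the interval is -0.26 to +0.02.

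Phase 1 also gives current Jadelle use as about 4%. For 4% versus 15%, power is 76% unclustered, 54% with the design effect, and 35% to 36% on 4 df.

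**Step 5: the tests actually planned.** Beta-binomial simulation, 200,000 runs, clusters of 33, 33 and 34 per arm, ICC 0.02; the Fisher switch here applies when any observed cell is below 5.

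| | Chi-square | Chi-square with Fisher switch |
|---|---|---|
| Rejection, 3% vs 15% | 83% | 80% |
| Type I error, both arms 3% | 10.6% | 4.5% |
| Both arms 4% | 11.1% | 5.9% |
| Both arms 9% | 12.9% | 11.2% |
| Both arms 15% | 13.0% | 13.0% |

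**The case against.** The strongest reply is that the 36% miss rate belongs to a cluster-adjusted analysis the protocol does not plan. Under the planned tests, rejection at 3% versus 15% is 80% to 83%. With the Fisher switch, type I error at the Jadelle rates the documents give (3% and about 4%) is 4.5% to 6%. The protocol does not say whether cell sizes means observed or expected counts; if expected, rejection is about 83% and type I error 5.1% at 3% and 7.4% at 4%. So, near the planning null, the planned tests behave better than the adjusted power suggests.

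That is accurate, and it limits the consequence. It does not save the statement, which ties 85% power to an ICC of 2%; no calculation in the document does that. The near-nominal error comes from Fisher's conservatism with sparse cells, and it is lost at common rates of 9% to 15% (rates assumed here as the midpoint and upper end of the planning range).

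Two further points stand as cautions. The protocol names no 4-df test, so the 42% to 44% illustrates what six clusters imply; the figure that follows from the protocol's own formula is 64%. The revised interval is a simple normal one, whereas the printed output cites a log method; the two agree only to the printed decimals. The 4% control rate is a sensitivity check and is not needed for the conclusion.

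**Conclusion.** The statement is wrong as written. The 85% is the power for individual randomization. With the protocol's own ICC and six clusters it is about 64% by the same formula, so the chance of missing the planned effect is about 36%, more than double the 15% implied. This rests on equal cluster sizes, which is favourable, and on the protocol's ICC of 2%, for which it gives no justification. It applies to an analysis that accounts for clustering. It must be corrected, because it is the only power figure in the document and its own printed output contradicts it.

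**What to change.** Replace the power statement in Phase 1 and in Methods & Models with text such as:

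> 200 women in six clusters (about 33 each, equal sizes assumed), ICC 0.02, design effect 1.65, effective sample size about 61 per arm. Power for 3% versus 15% Jadelle uptake is about 64% by the normal approximation and about 42% to 44% with a cluster-level t test on 4 df. The rate detectable from 3% with 85% power is about 20% (normal) or 28% to 30% (4 df).

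State that this power refers to a cluster-adjusted analysis, and name that analysis in the Analysis Plan. Once it is named, present the matching power as the trial's figure and the other as supporting information.

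Reprint the precision table with the design effect: SE 0.051, 95% interval -0.22 to -0.02 (normal) or -0.26 to +0.02 (4 df), stating the method used. Either justify the 3% control rate in a sentence or add the 4% versus 15% figures (about 54% normal, 35% to 36% on 4 df).

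The cost is wording in two places, a named analysis, one reprinted table and a less favourable stated power. Enrolment and the number of clusters do not change.
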